9.4 Sample Size Determination

Two scenarios with different underlying good/poor performer proportions were simulated (see figures 3 and 4): 50/50 and 40/60. $\geq 80\%$ power is obtained under both scenarios. Higher specificity and sensitivity would increase the power. Increasing the total number of subjects would also increase power.

[figure not shown]

Figure 4: Power calculations for a 40%/60% good/poor performer scenario.

Based on sample size calculations, a total of 30 eligible subjects are required to provide $>80\%$ power to reject the null hypothesis for the statistical test for the primary objective.

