4.2.2 Clinical Data

Fraysse & James (2020) provided a basis and background for the current work. Notably, a simple outcome model and population statistics for sentence recognition scores for cochlear implant patients at the Toulouse clinic were presented. Figure 2 gives scores in quiet at 1 day and 1 month, using CI alone for a sequence of 61 patients.

[figure not shown]

Figure 2: Sentence recognition scores in quiet at 65 dB SPL using CI alone for a sequence of 61 implanted patients.

One can observe the large variability in raw sentence recognition scores at 1-day and at 1-month after activation. Fraysse and James present a simple model for likely sentence recognition scores at 1 month assuming correct electrode placement (in terms of depth and scala position): Using data from a previous study of a series of 118 patients (James et al, 2018), median score at 1 month was approximately 72/100 if certain patient-related parameters were not accounted for. However, if both duration of deafness and etiology effects were corrected for, then median scores increased to greater than or equal to 90/100. 90/100 therefore indicates a level of performance for CI subjects which one may associate with an absence of limiting factors as introduced earlier.

Figure 2 is for a continuous sequence of CI subjects: 16/61 scored >90/100 at one month. These were unfiltered for any patient-related parameter or device type. The two studies indicate that 30-50 percent of subjects should achieve the target optimal score of 90/100 at one month in a new sample.

Fraysse and James also proposed that scores in quiet at 1 day using CI alone could be useful to predict outcomes. Using the data in Figure 2 as an example, those subjects scoring $\geq 60/100$ at 1 day were ~ 14 times more likely to score $\geq 90/100$ at 1 month compared with those who did not. This

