7.1.1 Design Rationale

The aim is to recruit all CI patients with a Nucleus device who have been evaluated since the centre's specific test battery was implemented in 2019. This includes some patients implanted as long ago as 2016. The centre implants approximately 25 eligible adult patients per year. As such therefore there is no bias in the selection of patients. Unilateral deaf or single-sided deaf CI recipients are excluded since natural hearing may interfere with the measure of performance of the implanted ear. Similarly, subjects who received bilateral cochlear implants will be included but their sentence recognition scores only considered for the first ear implanted up until they received the second implant.

Subjects with a cognitive impairment will also be included since the evaluation of cognitive function is one of the aims of the test battery.

The Toulouse centre has extensively studied early performance indicators of CI recipients, as well as looking at prognosis of performance in the long-term. Extension of the implications of the study findings to the long term is one of the exploratory objectives of the study, as is the subjective evaluation of performance by the recipients themselves.

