7.2.3 Number of Subjects Required

For a test battery that has an underlying moderate specificity and sensitivity of ~80%, a total of 30 subjects should be sufficient to conclude that there is a relationship between pass/fail outcome of the battery (cumulatively – fail on any test -> fail) and good/poor performance based on sentence test score criterion. Therefore, we aim to recruit 30 or more subjects.

The sample size calculation is to be found in section 9.3.1.

All patients implanted since the centre started using their specific test battery will be screened for eligibility. The centre's staff currently estimate that 30 or more patients are eligible.

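### Does leaving the centre's own 26% good-performer rate out of the power scenarios undermine the sample size of 30?

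*Combined protocol and SAP*

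**What the plan says.** Section 9.4 describes the basis for the sample size: "Two scenarios with different underlying good/poor performer proportions were simulated (see figures 3 and 4): 50/50 and 40/60". It reports at least 80% power in both and concludes that 30 eligible subjects suffice. Section 7.2.3 gives the accuracy behind this: "For a test battery that has an underlying moderate specificity and sensitivity of ~80%, a total of 30 subjects should be sufficient". It also sets the target as 30 or more.

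The evidence on the split is in section 4.2.2. For the 61-patient consecutive series, "16/61 scored >90/100 at one month", and "These were unfiltered for any patient-related parameter or device type". For the other series, of 118 patients, "median score at 1 month was approximately 72/100 if certain patient-related parameters were not accounted for", but "if both duration of deafness and etiology effects were corrected for, then median scores increased to greater than or equal to 90/100". The section then concludes: "The two studies indicate that 30-50 percent of subjects should achieve the target optimal score of 90/100 at one month in a new sample".

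Section 9.2.1 defines a good performer by a score of 90 or more. Section 9.3.1 names chi-squared at alpha 0.05 as the test, with Fisher's exact test if a cell holds too few subjects. Section 9.6 names both tests without repeating that condition.

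**The concern.** The only raw good-performer rate in the document is 26%, and both planning splits exceed it. The lower end of the document's own expected range, 30%, was not simulated either. The 50% end appears to match a median of 90 that was reached only after correction for duration of deafness and etiology. The study will classify raw scores, sets no limit on duration of deafness or etiology, and says that "Subjects with a cognitive impairment will also be included".

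A lopsided split costs power in a 2x2 table and thins out the smallest cell. If power fell below 80% at a realistic split, 30 subjects would be too few. A sparse table also makes Fisher's test the likely primary test, and the plan does not say what count triggers it. An analyst could then choose between the two tests after seeing the table.

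**Working it through.** **Inputs.** N = 30 and the splits 50/50 and 40/60 (section 9.4); sensitivity and specificity 0.80 (section 7.2.3); alpha 0.05 (section 9.3.1), taken as two-sided because the test is non-directional; 16 of 61 (section 4.2.2).

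**Observed rate.** 16/61 = 0.262, exact (Clopper-Pearson) 95% interval 0.158 to 0.391.

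**Power formula.** Let π be the good-performer rate, g the number of good performers, a the good performers who pass the battery, and d the poor performers who fail it. Then

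power = Σ over g, a, d of Bin(g; 30, π) × Bin(a; g, 0.8) × Bin(d; 30−g, 0.8) × [p < 0.05],

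with p from the 2x2 table with rows (a, g−a) and (30−g−d, d). Every table is enumerated. The mixed rule uses Fisher if any expected count is below 5, otherwise uncorrected chi-squared; the threshold of 5 is an assumption.

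| Good-performer rate | Chi-squared, uncorrected | Fisher | Mixed rule |
|---|---|---|---|
| 50% (plan) | 0.937 | 0.888 | 0.927 |
| 40% (plan) | 0.929 | 0.882 | 0.911 |
| 30% | 0.896 | 0.847 | 0.859 |
| 26.2% (16/61) | 0.872 | 0.819 | 0.825 |

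The first two rows reproduce the plan's statement. The last two show that it also holds at the low end of the expected range and at the observed rate. With the split fixed at 8/22 (30 × 0.262 = 7.9), power is 0.903 for chi-squared and 0.866 for Fisher.

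**Is 26% the endpoint's rate?** The 16 scored above 90; the endpoint includes 90. The number at exactly 90 is not given, so a range is needed:

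- one such patient: 17/61 = 27.9%, exact upper limit 40.8%, so 40/60 is no longer excluded;
- three: 19/61 = 31.1%, inside 30-50%;
- nine: 25/61 = 41.0%, above the lower planning split.

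**How sparse are the tables?** At 26.2%, the expected number of good performers is 30 × 0.262 = 7.87, and of passes 0.8 × 7.87 + 0.2 × 22.13 = 10.72. The smallest expected count under independence is 7.87 × 10.72 / 30 = 2.81. At 40% it is 12 × 13.2 / 30 = 5.28. The mixed rule sends 92% of samples to Fisher at 26.2%, 49% at 40% and 28% at 50%.

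**Does the missing threshold matter?** Uncorrected chi-squared and Fisher disagree in 5.3%, 4.8% and 5.0% of studies at 26.2%, 40% and 50%. That would be the exposure only if the analyst were free to pick either test for any table. Section 9.3.1 puts chi-squared first and Fisher for sparse cells. The two usual readings of sparse (any expected count below 5; any observed count below 5) lead to different conclusions in 0.6%, 3.0% and 3.9% of studies. At the rate that prompted the concern, the ambiguity almost vanishes, because both readings lead to Fisher.

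**The case for a change.** The best case for a change is that the margin at 26% is thin. Under the mixed rule, 78% sensitivity and specificity still give 0.86 at 40/60 but only 0.76 at 26.2%. The chance of seven or fewer good performers is 45% at 26.2%, against 4.4% at 40%, and a 7/23 split gives Fisher power of 0.79. If the true rate were 40%, 16 or fewer of 61 would occur with probability 0.018. Yates-corrected chi-squared at 26.2% gives 0.749, below target. The remedy would be a few lines of text.

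The figures stand, but they do not show that the plan is wrong:

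- The 78% and 7/23 results move an input away from what the plan assumes, or condition on an unlucky draw. Averaged over all draws at 80%, power exceeds 80%. The more sensitive assumption is accuracy: at 75% for both, Fisher power is already 0.70 at 40/60. A further split would not address that.
- The 0.018 compares a rate for scores above 90 with an endpoint of 90 or more. The new sample also differs from the 61: it is restricted by device and excludes single-sided deafness, with an unknown effect on the rate.
- The share reaching 90 in the 118-patient series is not given. An uncorrected median near 72 shows only that it is below half, which is compatible with 40%.
- The Yates figure applies the correction to every table, sparse ones included. The plan sends sparse tables to Fisher and nowhere mentions a continuity correction.

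What remains is that 26% sits awkwardly beside 30-50%, and that neither 26% nor 30% was simulated. A line on either would be harmless, but it would alter no result.

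**Conclusion.** The power statement is correct for the two splits in section 9.4 and stays correct at the centre's 26%: 0.82 with Fisher, 0.87 with uncorrected chi-squared. Adding a lower split would leave 30 subjects, the endpoint and the analysis as they are. The open Fisher threshold is a gap that an analyst would fill by convention, with an effect of 0.6% of studies at 26% and at most about 4% at the planned splits.

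This rests on sensitivity and specificity of 80%, a two-sided 0.05 level, no continuity correction, and a good-performer rate not much below 26%. Figures 3 and 4 could not be seen, so no view is taken on what support they give for the 80%. For a single-centre, non-interventional feasibility study with a target of 30 or more, no change to the plan is called for.

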9.5 Analysis Population

There are no sub-populations.

9.6 Primary Endpoint Analyses

The contingency table between good/poor performer and pass/fail of processing tests will be analysed using a chi-squared or Fischer's exact tests.

9.7 Secondary Endpoint Analyses

Not applicable.

9.8 Exploratory Endpoint Analyses

Parametric (e.g., Students t) or non-parametric (e.g., Mann-Whitney U) tests will be used to test differences between groups depending on normal or non-normal value distributions.

Parametric or non-parametric correlation tests, or linear models will be used to test relationships between variables depending on normal or non-normal value distributions.

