7.2 Subjects

7.2.1 Inclusion Criteria

Subjects must meet all the inclusion criteria described below to be eligible for this clinical investigation.

- 1) Adult subjects, 18 years or older
- 2) Subjects unilaterally implanted or bilaterally implanted with at least 6 months separating the two cochlear implantations.
- 3) Subjects who have been implanted between January 2016 and December 2021.
- 4) Subjects have received a Nucleus CI: CI512, CI522 or CI532 cochlear implants with non-rotating magnet, or CI600 series equivalent CI612, CI622 and CI632 with rotating magnet and external sound processors CP900 or CP1000 behind-the-ear, or Kanso or Kanso 2 off-the-ear types.
- 5) Subjects who are fluent in French (language used in the questionnaire and speech tests)
- 6) Subjects who are not opposed to participating in the study
- 7) Subjects for whom the medical record data is available throughout the defined data search period.

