7.2.5 Recruitment and Study Duration

The following subject status definitions apply:

- *Enrolled*: A subject who is has not opposed to participation in the study.
- *Screen Fail*: An Enrolled subject that has been determined to not meet one or more eligibility criteria.
- *Participated*: Has provided answers to the patient questionnaire.
- *Withdrawn*: Not applicable.
- *Completed*: Enrolled subjects who completed the patient questionnaire.

The recruitment period for the clinical investigation is estimated to be approximately 3 months from the time of first subject enrolled to the last subject.

Recruitment of subjects shall be performed in a back-chronological order from the cochlear implantation surgery. Recruitment shall start with the last subject that has undergone this procedure in the year 2021 and chronologically working backwards until recruitment targets are met.

This process will avoid any recruitment bias.

The expected duration of each subject's participation in the clinical investigation is the time it takes for the subject to read and discuss the non-opposition form with the study team, complete and return the questionnaire. Time for completing the questionnaire is estimated to be 30-40 minutes.

Clinical Investigation completion is defined as the recording and completion of the last medical record search for the last enrolled subject in the electronic Case Report Forms (eCRF).

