7.3.2 Self-reported performance (at time of recruitment)

The SSQ12 questionnaire will be used. The Speech, Spatial, and Qualities of Hearing Scale questionnaire (SSQ-12) (Noble et al, 2013) was developed in the MRC Institute of Hearing Research, UK, and is a scaled-down version of the 49 items SSQ questionnaire (Gatehouse & Noble, 2004). It is designed to compile a sub-set of items from the longer original 49 version to represent the scale as a whole, measuring self-reported auditory disability, reflecting the reality of hearing in the everyday world. It has been shown to provide similar results to SSQ-49 (Noble et al, 2013). It covers:

- Hearing speech in a variety of competing contexts
- The directional, distance and movement components of spatial hearing
- Segregation of sounds and attending to simultaneous speech streams
- Ease of listening
- The naturalness, clarity and identifiability of different speakers, different musical pieces and instruments, and different everyday sounds.

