9.2.3 Exploratory Endpoints

- Sentence recognition score at 1-day in quiet.
- SSQ12 score at time of inclusion.
- Sentence recognition score at 1-month: In quiet and in fixed levels of babble 10 dB & 5 dB SNR, and SNR50.
- Score/s at 1-day, 1-month, and later time points post activation up until the time of recruitment for various fixed SNRs.

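### SSQ12 is answered after a different length of implant use by each subject, but the pass/fail comparison does not adjust for time since activation

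*Combined protocol and SAP*

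**What the plan says.** Section 9.2.3 lists "SSQ12 score at time of inclusion" as an exploratory endpoint, and section 7.3.2 also places the questionnaire at recruitment. It is answered once. On calendar time, section 7.2.5 says "The recruitment period for the clinical investigation is estimated to be approximately 3 months", while criterion 3 in section 7.2.1 admits "Subjects who have been implanted between January 2016 and December 2021".

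Section 9.3.3.1 compares three outcomes between subjects who pass and who fail the test battery: the sentence score in quiet at 1 day, the sentence score at 10 dB SNR at 1 month, and SSQ12. The first two are fixed relative to activation; SSQ12 is not. Section 9.8 treats all three alike: "Parametric (e.g., Students t) or non-parametric (e.g., Mann-Whitney U) tests will be used to test differences between groups", with the choice depending on the distribution. Its next sentence allows linear models, but for relationships between variables, and it names no covariate.

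Section 9.1 places longitudinal sentence scores on a standard follow-up grid. It makes no such provision for SSQ12. No section uses time since activation as a covariate, a stratifier or a restriction.

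**The concern.** Questionnaire dates fall close together while implant dates do not, so SSQ12 compares people at different stages of implant use. Two things could follow.

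- **Loss of precision.** If SSQ12 changes with use, variation in length of use goes into the error term of the two-sample test.
- **Bias.** If, in addition, the pass and fail groups differ in mean time since activation, part of the difference credited to the battery result is due to length of use. Section 7.3.3.5 lets the cognitive tests be done at any point after surgery. Section 7.1.1 says the battery began in 2019 and, of the patients evaluated with it, "This includes some patients implanted as long ago as 2016". Early recipients may thus have had some battery tests much later after surgery than recent ones, so battery result and implant date could be related. With 30 subjects, chance imbalance is also possible.

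At stake is how to read the SSQ12 comparison, which rests on the study's only prospective measurement.

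**Working it through.** **The plan's own figure.** The documents give no power figure for SSQ12. The only one is more than 80% for the primary contingency-table test at N=30 (section 9.4). With 80% sensitivity and specificity, exact power for the 50/50 and 40/60 splits is 93.7% and 92.9% (Pearson), 88.8% and 88.2% (Fisher), and 87.1% and 85.5% (Yates). The stated bound is met. It has no bearing on this point.

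**Step 1: spread in length of use.**
- Narrow case. Section 7.2.5 says "Recruitment shall start with the last subject that has undergone this procedure in the year 2021" and works backwards. Section 7.3.1 contacts the target plus 20% in a first draw: 30 × 1.2 = 36. Section 7.1.1 says "The centre implants approximately 25 eligible adult patients per year". The span is 36/25 = 1.44 years, about 17 months.
- Wide case. January 2016 to December 2021 is 6 × 12 = 72 months.
- The narrow case may be optimistic. Among all patients implanted since the battery began, the centre expects only that at least 30 are eligible (section 7.2.3), and section 7.1.1 expects some implants from 2016.

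**Step 2: share of SSQ12 variance explained by time.** Assumptions not in the documents: residual SD 1.8 points, time uniform over the span, linear slope b in points per year. Then SD(time) = span/√12 and R² = b²·SD² / (b²·SD² + 1.8²), with 1.8² = 3.24.

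| Span | SD² (years²) | b = 0.4 | b = 0.6 |
|---|---|---|---|
| 1.44 years | 1.44²/12 = 0.173 | 0.028/3.268 = 1% | 0.062/3.302 = 2% |
| 5.75 years (0.25 to 6) | 5.75²/12 = 2.755 | 0.441/3.681 = 12% | 0.992/4.232 = 23% |

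Over the narrow span, R² = 10% needs b = √(3.24 × 0.10/0.90/0.173) ≈ 1.4 points per year, and R² = 30% needs b = √(3.24 × 0.30/0.70/0.173) ≈ 2.8.

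**Step 3: possible bias.** Bias = b × difference in mean time between groups. Over 1.44 years, even complete separation of two equal groups gives a difference of only 1.44/2 = 0.72 years, so the bias is at most 0.4 × 0.72 = 0.29 or 0.6 × 0.72 = 0.43 points. Imbalances of 1 or 2 years need a wider span.

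**Step 4: simulation of the comparison.** N=30 split 15/15 (assumed), 4,000 runs per setting, residual SD 1.8, time over 0.25 to 6 years (the wide case). An unadjusted t-test is set against a linear model with a linear term for time.

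Type I error at nominal 0.05:

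| Slope (points/year) | Difference in mean time | Bias (points) | Unadjusted | Adjusted |
|---|---|---|---|---|
| 0 | 0, 1 or 2 years | 0 | 0.046–0.053 | 0.045–0.048 |
| 0.2 or 0.4 | 0 | 0 | 0.054 | 0.052 |
| 0.2 | 1 year | 0.2 | 0.062 | 0.050 |
| 0.2 | 2 years | 0.4 | 0.089 | 0.052 |
| 0.4 | 1 year | 0.4 | 0.082 | 0.048 |
| 0.4 | 2 years | 0.8 | 0.192 | 0.054 |

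Power with balanced groups and an assumed true difference of 2 points:

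| Slope | Unadjusted | Adjusted |
|---|---|---|
| 0 | 0.83 | 0.81 |
| 0.2 | 0.83 | 0.83 |
| 0.4 | 0.79 | 0.82 |
| 0.6 | 0.73 | 0.83 |

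If time has no effect, adjustment costs about 2 points of power. At the steepest slope over the widest span it gains about 10.

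**The case against.** The strongest reply is that nothing in the documents says SSQ12 changes with use. A reader might take section 4.1 as showing that it does, because speech recognition in noise may go on improving. That remark concerns speech tests in noise, and the same sentence says word scores in quiet have often levelled off. The plan's one remark on SSQ12 over time, in section 4.3, is that scores vary widely at one to six years. That is spread between people, not a trend. This objection stands, and it is why no size can be given.

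Imbalance between the groups is also only a possibility. Aided thresholds are taken soon after activation and datalogging covers activation to 1 month, so these components are early; only the cognitive tests are expressly free in timing. Back-chronological recruitment may keep the span narrow, and then Steps 2 and 3 leave little to correct. The even 15/15 split is assumed too. Failing any one of nine tests fails the battery, so the groups could be very unequal.

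It can also be said that section 9.8 gives its tests as examples and permits linear models, and that age or duration of deafness could equally be proposed as covariates. The first part narrows the gap without closing it, because the models are not assigned to group differences and a covariate chosen after seeing the data is weaker. As to the second, time since activation has a particular claim: the plan's own timing of SSQ12 creates the variation. The battery result cannot alter the implant date, so time is not a mediator and adjusting for it removes no part of the effect of interest.

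**Conclusion.** The point holds as a minor, inexpensive improvement to an exploratory analysis. Length of use at SSQ12 differs by about 17 to 72 months across subjects, and the planned group test ignores it. Precision is lost only if SSQ12 changes with use; bias needs group imbalance as well. Under the assumed slopes and the wide span, unadjusted type I error is 0.062 to 0.082 with a 1-year imbalance and 0.089 to 0.192 with 2 years, while the adjusted analysis stays near 0.05. With balanced groups or no trend there is no inflation. Over the narrow span the effect may be negligible.

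A reader might assume that time explains 10–30% of SSQ12 variance and so infer that adjustment is worth 1/(1 − R²) = 1.11 to 1.43 times the sample. The documents do not support that: over 17 months it would need about 1.4 to 2.8 points per year under the assumed SD, and no such trend is given. Nor do they show that the planned comparison is in fact confounded.

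The primary endpoint and its sample size are not affected.

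**What to change.** In section 9.8, state that the SSQ12 pass/fail comparison in 9.3.3.1 will use a linear model containing battery result and log time from activation to questionnaire, fitted on ranks if the scores are clearly non-normal. Report the distribution of that time by pass/fail group, so that readers can see whether there is an imbalance.

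For the SSQ12–SNR50 relationship in 9.3.3.4, keep the planned analysis and give a time-adjusted estimate only as a sensitivity analysis. If both measures improve with use, that shared change is part of the relationship being asked about, and forcing the covariate in would change the question.

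The cost is SAP wording and one degree of freedom, about 2 points of power at N=30 in the simulation if time has no effect. Surgery date already drives recruitment order, and the datalogging and 1-month measures are counted from activation, so the interval should be derivable from the records. No section lists activation date as a data item, however, so confirm that the eCRF captures both it and the questionnaire date.
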